## 10. SUMMARY TABLES, FIGURES, AND LISTINGS

Summary tables and figures are numbered following the International Council on Harmonization (ICH) structure but may be renumbered as appropriate during the compilation of the tables and figures for the CSR. Note that all summary tables and figures will be generated using SAS® Version 9.4 or higher, as appropriate.

In-text tables and figures will be generated as RTF and all other tables and listings will be generated as SAS® LST format and converted to MS Word for inclusion in the CSR. In compliance with Celerion Procedure Guides (PG)/SOPs, SAS® outputs will not be manually edited.

### 10.1 In-text Summary Tables and Figures

The following is a list of table and figure titles that will be included in the text of the CSR. Tables and figures will be numbered appropriately during compilation of the CSR.

#### **Section 10:**

Number	Title	Shell
Table 10-1	Disposition Summary (Safety Population)	IDS

#### **Section 11:**

Number	Title	Shell
Table 11-1	Demographic Summary (Safety Population)	IDEM
Table 11-2	Summary of Serum TRL345 Pharmacokinetic Parameters Following Administration of a Single 1-Hour Intravenous Infusion of TRL345 (Pharmacokinetic Analysis Population)	ITPPar1
Table 11-3	Summary of Serum TRL345 ADA Detection Following Administration of a Single 1-Hour Intravenous Infusion of TRL345 or Placebo (Immunogenicity Population)	IIST
Figure 11-1	Arithmetic Mean Serum TRL345 Concentration Versus Time Profiles Following Administration of a Single 1-Hour Intravenous Infusion of TRL345 (Linear Scale) (Pharmacokinetic Analysis Population)	PFPConc2

## **Section 12:**

Number	Title	Shell
Table 12-1	Treatment-Emergent Adverse Event Frequency by Treatment - Number of Subjects Reporting the Event (% of Subjects Dosed) (Safety Population)	IAES

## **10.2 Section 14 Summary Tables and Figures**

The following is a list of table and figure titles that will be included in Section 14 of the report. Table and figure titles may be renumbered as appropriate during the compilation of the report.

### **14.1 Demographic Data Summary Tables**

Number	Title	Shell
Table 14.1.1	Disposition Summary (Safety Population)	CDS
Table 14.1.2	Demographic Summary (Safety Population)	CDEM

### **14.2 Pharmacokinetic and Immunogenicity Data Summary Tables and Figures**

#### **14.2.1 Serum TRL345 Tables**

Number	Title	Shell
Table 14.2.1.1	Serum TRL345 Concentrations (µg/mL) Following Administration of a Single 1-Hour Intravenous Infusion of 1 mg/kg TRL345 (Treatment A) (Pharmacokinetic Analysis Population)	CPConc1
Table 14.2.1.2	Serum TRL345 Concentrations (µg/mL) Following Administration of a Single 1-Hour Intravenous Infusion of 10 mg/kg TRL345 (Treatment B) (Pharmacokinetic Analysis Population)	CPConc1
Table 14.2.1.3	Serum TRL345 Concentrations (µg/mL) Following Administration of a Single 1-Hour Intravenous Infusion of Matching Placebo (Treatment P) (Pharmacokinetic Analysis Population)	CPConc1
Table 14.2.1.4	Serum TRL345 Pharmacokinetic Parameters Following Administration of a Single 1-Hour Intravenous Infusion of 1 mg/kg TRL345 (Treatment A) (Pharmacokinetic Analysis Population)	CPPar1

Number	Title	Shell
Table 14.2.1.5	Serum TRL345 Pharmacokinetic Parameters Following Administration of a Single 1-Hour Intravenous Infusion of 10 mg/kg TRL345 (Treatment B) (Pharmacokinetic Analysis Population)	CPPar1

## 14.2.2 Serum TRL345 Figures

Number	Title	Shell
Figure 14.2.2.1	Arithmetic Mean (SD) Serum TRL345 Concentration Versus Time Profiles Following Administration of a Single 1-Hour Intravenous Infusion of TRL345 (Linear Scale) (Pharmacokinetic Analysis Population)	PFPConc1
Figure 14.2.2.2	Arithmetic Mean Serum TRL345 Concentration Versus Time Profiles Following Administration of a Single 1-Hour Intravenous Infusion of TRL345 (Linear Scale) (Pharmacokinetic Analysis Population)	PFPConc2
Figure 14.2.2.3	Arithmetic Mean Serum TRL345 Concentration Versus Time Profiles Following Administration of a Single 1-Hour Intravenous Infusion of TRL345 (Semi-log Scale) (Pharmacokinetic Analysis Population)	PFPConc3

## 14.2.3 Serum TRL345 Immunogenicity Tables

Number	Title	Shell
Table 14.2.3.1	Serum TRL345 ADA Detection Summary Following Administration of a Single 1-Hour Intravenous Infusion of TRL345 or Placebo (Immunogenicity Population)	ADAD

## 14.3 Safety Data Summary Tables

### 14.3.1 Displays of Adverse Events

Number	Title	Shell
Table 14.3.1.1	Treatment-Emergent Adverse Event Frequency by Treatment – Number of Subjects Reporting the Event (% of Subjects Dosed) (Safety Population)	CAES
Table 14.3.1.2	Treatment-Emergent Adverse Event Frequency by Treatment – Number of Adverse Events (% of Total Adverse Events) (Safety Population)	CAEE

Number	Title	Shell
Table 14.3.1.3	Treatment-Emergent Adverse Event Frequency by Treatment, Severity, and Relationship to Study Product – Number of Adverse Events (Safety Population)	CAESR

#### **14.3.2 Listings of Deaths, other Serious and Significant Adverse Events**

Number	Title	Shell
Table 14.3.2.1	Serious Adverse Events (Safety Population)	16.2.7

#### **14.3.3 Narratives of Deaths, other Serious and Certain other Significant Adverse Events**

#### **14.3.4 Abnormal Laboratory Value Listing (each subject)**

Number	Title	Shell
Table 14.3.4.1	Out-of-Range Values and Recheck Results – Chemistry (Safety Population)	CLBO
Table 14.3.4.2	Out-of-Range Values and Recheck Results – Hematology (Safety Population)	

#### **14.3.5 Displays of Other Laboratory, Vital Signs, Electrocardiogram, Physical Examination, and Other Safety Data**

Number	Title	Shell
Table 14.3.5.1	Clinical Laboratory Summary and Change From Baseline – Chemistry (Safety Population)	CLBD
Table 14.3.5.2	Clinical Laboratory Shift From Baseline – Chemistry (Safety Population)	CLBS
Table 14.3.5.3	Clinical Laboratory Summary and Change From Baseline – Hematology (Safety Population)	CLBD
Table 14.3.5.4	Clinical Laboratory Shift From Baseline – Hematology (Safety Population)	CLBS
Table 14.3.5.5	Vital Sign Summary and Change From Baseline (Safety Population)	CVS
Table 14.3.5.6	12-Lead Electrocardiogram Summary and Change From Baseline (Safety Population)	CEG

### **10.3 Section 16 Data Listings**

Note: Hepatitis and HIV results that are provided by the clinical laboratory will not be presented in subject data listings and will not be included in any database transfer. All data will be presented as outlined in the CRF (i.e., time point information will be consistent with the CRF data).

Data listings are numbered following the ICH structure but may be renumbered as appropriate during the compilation of the TFLs for the CSR. The following is a list of appendix numbers and titles that will be included as data listings:

#### **16.1 Study Information**

##### **16.1.9 Statistical Methods**

Number	Title
Appendix 16.1.9.1	Statistical Analysis Plan

##### **16.1.10 Clinical Laboratory Reference Ranges**

Number	Title
Appendix 16.1.10.1	Clinical Laboratory Reference Ranges

#### **16.2 Subject Data Listings**

##### **16.2.1 Subject Discontinuation**

Number	Title
Appendix 16.2.1.1	Subject Disposition (Safety Population)

##### **16.2.2 Protocol Deviations**

Number	Title
Appendix 16.2.2.1	Protocol Deviations

##### **16.2.3 Subjects Excluded From the Pharmacokinetic and Immunogenicity Analysis**

Number	Title
Appendix 16.2.3.1	Subjects Excluded From the Pharmacokinetic Analysis
Appendix 16.2.3.2	Subjects Excluded From the Immunogenicity Analysis

Note: Appendices in sections 16.2.2 and 16.2.3 are generated in MS Word for inclusion in the CSR.

#### 16.2.4 Demographic Data

Number	Title
Appendix 16.2.4.1	Demographics (Safety Population)
Appendix 16.2.4.2	Physical Examination (I of II) (Safety Population)
Appendix 16.2.4.3	Physical Examination (II of II) (Safety Population)
Appendix 16.2.4.4	Physical Examination Descriptions (Safety Population)
Appendix 16.2.4.5	Medical History (Safety Population)
Appendix 16.2.4.6	Substance Use (Safety Population)

#### 16.2.5 Compliance and/or Drug Concentration Data

Number	Title
Appendix 16.2.5.1	Subject Eligibility (Safety Population)
Appendix 16.2.5.2	Test Compound Description
Appendix 16.2.5.3	Test Compound Administration Times (Safety Population)
Appendix 16.2.5.4	Prior and Concomitant Medications (Safety Population)
Appendix 16.2.5.5	Pharmacokinetic Blood Draw Times and Serum TRL345 Concentration Data (Safety Population)
Appendix 16.2.5.6	Immunogenicity Blood Draw Times and ADA Results (Safety Population)
Appendix 16.2.5.7	Interleukin-1 Alpha Blood Draw Times and Concentration Data (Safety Population)
Appendix 16.2.5.8	Pharmacodynamic Blood Draw Times (Safety Population)
Appendix 16.2.5.9	Possible Exploratory Analyses Data Blood Draw Times (Safety Population)

#### 16.2.6 Individual Efficacy/Pharmacokinetic/Pharmacodynamic Response Data

Number	Title	Shell
Appendix 16.2.6.1	Individual Serum TRL345 Concentration Versus Time Profiles Following Administration of a Single 1-Hour Intravenous Infusion of TRL345 (Linear and Semi-log Scale) Subject <#>	PFPConc5

Number	Title	Shell
Appendix 16.2.6.2	Intervals (Hours) Used for Determination of Serum TRL345 Kel Values (Pharmacokinetic Analysis Population)	CPKel2

### 16.2.7 Adverse Events Listings

Number	Title
Appendix 16.2.7.1	Adverse Events (Safety Population)
Appendix 16.2.7.2	Details for Serious Adverse Events (Safety Population) This listing will be removed if no serious adverse events are reported.

### 16.2.8 Clinical Laboratory Reports

Number	Title
Appendix 16.2.8.1	Clinical Laboratory Report - Chemistry (Safety Population)
Appendix 16.2.8.2	Clinical Laboratory Report - Hematology (Safety Population)
Appendix 16.2.8.3	Clinical Laboratory Report - Coagulation (Safety Population)
Appendix 16.2.8.4	Clinical Laboratory Report - Urine Drug Screening (Safety Population)
Appendix 16.2.8.5	Clinical Laboratory Report - Other (Safety Population)
Appendix 16.2.8.6	Vital Signs (Safety Population)
Appendix 16.2.8.7	12-Lead Electrocardiogram (Safety Population)
Appendix 16.2.8.8	12-Lead Electrocardiogram – Average of Triplicates (Safety Population)

## **11. TABLE, FIGURE, AND LISTING SHELLS**

The following table shells provide a framework for the display of data from this study. The shells may change due to unforeseen circumstances. These shells may not be reflective of every aspect of this study, but are intended to show the general layout of the tables that will be presented and included in the final report. Unless otherwise noted, all in-text tables will be presented in Times New Roman font size 9 and post-text tables will be presented in Courier New font size 9. In-text tables and figures will be generated as RTF and all other tables and listings will be generated as SAS® LST format and converted to MS Word for inclusion in the CSR. In compliance with Celerion PGs/SOPs, SAS® outputs will not be manually edited. Tables and figures will be generated from ADaM datasets created in accordance with CDISC guidance (ADaM Model 2.1 and ADaM implementation Guide 1.1).

## 11.1 In-text Summary Tables Shells

**Table IDS Disposition Summary (Safety Population)**

	Treatment				
Category	P	A	B	Active Total	Overall
Dosed	XX (XX%)	XX (XX%)	XX (XX%)	XX (XX%)	XX (XX%)
Completed Study	XX (XX%)	XX (XX%)	XX (XX%)	XX (XX%)	XX (XX%)
Discontinued From Study	XX (XX%)	XX (XX%)	XX (XX%)	XX (XX%)	XX (XX%)
<Reason>	XX (XX%)	XX (XX%)	XX (XX%)	XX (XX%)	XX (XX%)
Treatment A: A single 1-hour intravenous infusion of 1 mg/kg TRL345 (Dose Group 1) Treatment B: A single 1-hour intravenous infusion of 10 mg/kg TRL345 (Dose Group 2) Treatment P: A single 1-hour intravenous infusion of matching placebo (Dose Groups 1 and 2)  Source: Table 14.1.1 Program: /CAXXXXX/sas_prg/stsas/intext/t_disp.sas DDMMMYYYY HH:MM					

**Table IDEM Demographic Summary (Safety Population)**

Trait	Category/Statistic	Treatment			Active Total	Overall
		P	A	B		
Sex	Female	XX (XX%)	XX (XX%)	XX (XX%)	XX (XX%)	XX (XX%)
	Male	XX (XX%)	XX (XX%)	XX (XX%)	XX (XX%)	XX (XX%)
Race	Asian	XX (XX%)	XX (XX%)	XX (XX%)	XX (XX%)	XX (XX%)
	Black or African American	XX (XX%)	XX (XX%)	XX (XX%)	XX (XX%)	XX (XX%)
	White	XX (XX%)	XX (XX%)	XX (XX%)	XX (XX%)	XX (XX%)
Ethnicity	Hispanic or Latino	XX (XX%)	XX (XX%)	XX (XX%)	XX (XX%)	XX (XX%)
	Not Hispanic or Latino	XX (XX%)	XX (XX%)	XX (XX%)	XX (XX%)	XX (XX%)
Age (yr)	n	X	X	X	X	X
	Mean	X.X	X.X	X.X	X.X	X.X
	SD	X.XX	X.XX	X.XX	X.XX	X.XX
	Minimum	XX	XX	XX	XX	XX
	Median	X.X	X.X	X.X	X.X	X.X
	Maximum	XX	XX	XX	XX	XX
	Range	XX	XX	XX	XX	XX
Body Mass Index (kg/m  )	n	X	X	X	X	X
	Mean	X.X	X.X	X.X	X.X	X.X
	SD	X.XX	X.XX	X.XX	X.XX	X.XX
	Minimum	XX	XX	XX	XX	XX
	Median	X.X	X.X	X.X	X.X	X.X
	Maximum	XX	XX	XX	XX	XX
	Range	XX	XX	XX	XX	XX
Height (cm)	n	X	X	X	X	X
	Mean	X.X	X.X	X.X	X.X	X.X
	SD	X.XX	X.XX	X.XX	X.XX	X.XX
	Minimum	XX	XX	XX	XX	XX
	Median	X.X	X.X	X.X	X.X	X.X
	Maximum	XX	XX	XX	XX	XX
	Range	XX	XX	XX	XX	XX

Trait	Category/Statistic	Treatment			Active Total	Overall
		P	A	B		
Weight (kg)	n	X	X	X	X	X
	Mean	X.X	X.X	X.X	X.X	X.X
	SD	X.XX	X.XX	X.XX	X.XX	X.XX
	Minimum	XX	XX	XX	XX	XX
	Median	X.X	X.X	X.X	X.X	X.X
	Maximum	XX	XX	XX	XX	XX
	Range	XX	XX	XX	XX	XX
Treatment A: <> Treatment B: <> Treatment P: <> Descriptive statistics for body mass index, height, and weight are calculated using Screening measurements.  Source: Table 14.1.2 Program: /CAXXXXX/sas_prg/stsas/intext/t_dem.sas DDMMYYYY HH:MM						

**Table ITPPar1 Summary of Serum TRL345 Pharmacokinetic Parameters Following Administration of a Single 1-Hour Intravenous Infusion of TRL345 (Pharmacokinetic Analysis Population)**

Pharmacokinetic Parameters	Treatment	
	A (N = X)	B (N = X)
Param1 (units)	XXX.X (XX.X) [n=xx]	XXX.X (XX.X) [n=xx]
Param2 (units)	XXX.X (XX.X) [n=xx]	XXX.X (XX.X) [n=xx]
Param3 (units)	XXX.X (XX.X) [n=xx]	XXX.X (XX.X) [n=xx]
Param4 (units)	XXX.X (XX.X) [n=xx]	XXX.X (XX.X) [n=xx]
Treatment A: A single 1-hour intravenous infusion of 1 mg/kg TRL345 (Dose Group 1) Treatment B: A single 1-hour intravenous infusion of 10 mg/kg TRL345 (Dose Group 2) Treatment P: A single 1-hour intravenous infusion of matching placebo (Dose Groups 1 and 2) AUCs C max , C min , and C eo i, values are presented as geometric mean (geometric CV%). T max , T min , and T last values are presented as median (min, max). Other parameters are presented as arithmetic mean ± SD. Source: Tables 14.2.1.4 to 14.2.1.5 Program: /CAXXXXXX/sas prg/pksas/intext-pk-tables.sas DDMMMYYYY HH:MM		

**Notes for Generating the Actual Table:**

Presentation of Data:

- The following PK parameters will be presented in the following order and with following units for TRL345 after single 1-hour Intravenous infusion: AUC0-tlast (µg\*hr/mL), AUC0-inf (µg\*hr/mL), AUC%extrap (%), Cmin (µg/mL), Cmax (µg/mL), Ceoi (µg/mL), Tmax (hr), Tmin (hr), Tlast (hr), Kel (1/hr), t½ (hr), CL (L/hr), and Vss (L/Kg).
- N will be presented as an integer (with no decimal);
- Summary statistics will be presented with same precision as defined in post-text shells.

**Table IIST      Summary of Serum TRL345 ADA Detection Following Administration of a Single 1-Hour Intravenous Infusion of TRL345 or Placebo (Immunogenicity Population)**

	Treatment			
ADA Positive	P (N = X)	A (N = X)	B (N = X)	Active Total (N = X)
Baseline	X (XX%)	X (XX%)	X (XX%)	X (XX%)
Day 8	X (XX%)	X (XX%)	X (XX%)	X (XX%)
Day 29	X (XX%)	X (XX%)	X (XX%)	X (XX%)
Day 43	X (XX%)	X (XX%)	X (XX%)	X (XX%)
Day 76	X (XX%)	X (XX%)	X (XX%)	X (XX%)
Overall ADA Positive	X (XX%)	X (XX%)	X (XX%)	X (XX%)
Treatment A: A single 1-hour intravenous infusion of 1 mg/kg TRL345 (Dose Group 1) Treatment B: A single 1-hour intravenous infusion of 10 mg/kg TRL345 (Dose Group 2) Treatment P: A single 1-hour intravenous infusion of matching placebo (Dose Groups 1 and 2) ADA Positive: Subject with a confirmed positive ADA result. Baseline is the last measurement collected prior to start of dosing. Overall indicates the number of subjects who had a positive ADA result at one or more time point. Percentage is relative to the number of subjects (N) dosed ADA = Anti-drug antibody  Source: Table 14.2.3.1 Program: /CAXXXXX/sas prg/stsas/intext/PROGRAMNAME.sas DDMMYYYY HH:MM				

**Table IAES Treatment-Emergent Adverse Event Frequency by Treatment - Number of Subjects Reporting the Event (% of Subjects Dosed) (Safety Population)**

[figure not shown]
	Treatment				
Adverse Event	P (N = X)	A (N = X)	B (N = X)	Active Total (N = X)	Overall (N = X)
Number of Subjects With TEAEs	XX (XX%)	XX (XX%)	XX (XX%)	XX (XX%)	XX (XX%)
Number of Subjects Without TEAEs	XX (XX%)	XX (XX%)	XX (XX%)	XX (XX%)	XX (XX%)
Eye disorders	XX (XX%)	XX (XX%)	XX (XX%)	XX (XX%)	XX (XX%)
Visual blurred	XX (XX%)	XX (XX%)	XX (XX%)	XX (XX%)	XX (XX%)
Gastrointestinal disorders	XX (XX%)	XX (XX%)	XX (XX%)	XX (XX%)	XX (XX%)
Dyspepsia	XX (XX%)	XX (XX%)	XX (XX%)	XX (XX%)	XX (XX%)
Nausea	XX (XX%)	XX (XX%)	XX (XX%)	XX (XX%)	XX (XX%)
Musculoskeletal and connective tissue disorders	XX (XX%)	XX (XX%)	XX (XX%)	XX (XX%)	XX (XX%)
Back pain	XX (XX%)	XX (XX%)	XX (XX%)	XX (XX%)	XX (XX%)
Muscle cramps	XX (XX%)	XX (XX%)	XX (XX%)	XX (XX%)	XX (XX%)
Musculoskeletal pain	XX (XX%)	XX (XX%)	XX (XX%)	XX (XX%)	XX (XX%)
Nervous system disorders	XX (XX%)	XX (XX%)	XX (XX%)	XX (XX%)	XX (XX%)
Headache	XX (XX%)	XX (XX%)	XX (XX%)	XX (XX%)	XX (XX%)
Reproductive system and breast disorders	XX (XX%)	XX (XX%)	XX (XX%)	XX (XX%)	XX (XX%)
Vaginal discharge	XX (XX%)	XX (XX%)	XX (XX%)	XX (XX%)	XX (XX%)
Respiratory, thoracic and mediastinal disorders	XX (XX%)	XX (XX%)	XX (XX%)	XX (XX%)	XX (XX%)
Epistaxis	XX (XX%)	XX (XX%)	XX (XX%)	XX (XX%)	XX (XX%)
Skin and subcutaneous tissue disorders	XX (XX%)	XX (XX%)	XX (XX%)	XX (XX%)	XX (XX%)
Sweating increased	XX (XX%)	XX (XX%)	XX (XX%)	XX (XX%)	XX (XX%)

	Treatment				
Adverse Event	P (N = X)	A (N = X)	B (N = X)	Active Total (N = X)	Overall (N = X)
Treatment A: <> Treatment B: <> Treatment P: <> Although a subject may have had 2 or more adverse events, the subject is counted only once within a category. The same subject may appear in different categories. Adverse events are classified according to MedDRA Version 26.1. TEAEs = Treatment-emergent adverse events  Source: Table 14.3.1.1 Program: /CAXXXXX/sas_prg/sters/intext/t_ae.sas DDMMYYYY HH:MM					

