2.2 Endpoints

2.2.1 *Safety Endpoints*

- Incidence and severity of abnormal physical exam findings, serum chemistries and hematology, vital signs (temperature, blood pressure, heart rate), adverse events, and incidence of serious adverse events

2.2.2 *Pharmacokinetics*

- C_{max} , C_{min} , CL, Vss, and T1/2 overall and by DG will be determined by ELISA

2.2.3 *Immunogenicity*

- Incidence of baseline and IP-emergent ADA (i.e., anti-TRL345 antibodies) in serum will be determined by ELISA

2.2.4 *Pharmacodynamics*

- The proportion of samples with TRL345 concentrations within prespecified ranges that are associated with neutralization of HCMV in human serum

2.2.5 *Exploration of Possible Off-Target Binding*

- Gastrointestinal and CNS adverse events will be compared across DGs for any qualitative or quantitative differences in such events. LDH, hsCRP, IL-1alpha, estimated AUC, and estimated T1/2 will also be compared across DGs.

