Serum for PK will be collected on Days 1 (0, 1, 2, 4, 6, 12 hours after start of infusion), 2 (24 hours after start of infusion) and 3 (48 hours after start of infusion), and on Days 8, 15, 29, 43 and 76. Additionally, serum samples will be taken on Days 1, 8, 29, 43 and 76 for measurement of anti-TRL345 antibody levels. Samples taken on Days 1, 43, and 76 will be analyzed using an electrochemiluminescence assay. Samples collected on Days 8 and 29 will be held for exploratory analysis, if warranted, based on Day 43 and Day 76 ADA analysis results. The proportion of subjects with detectable anti-TRL345 antibody responses prior to dosing and IP-emergent anti-TRL345 antibodies will be reported.

Additional serum samples will be collected on Days 1 (pre-infusion and 1 hour after start of infusion), 15, 29, 43, and 76 for *ex vivo* PD assessments, which will be conducted at [name] lab as defined in a separate protocol, whereby the dosed participants of the study will remain anonymous.

Additional serum samples will also be obtained on Days 1 (pre-infusion), 3, 8, 15, 29, and 43 for possible additional exploratory analyses that may be necessary to further explore any unexpected safety or tolerability observations.

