## 2. OBJECTIVES AND ENDPOINTS

Objectives	Endpoints
Primary	
To assess the safety and tolerability of TRL345 when administered intravenously (IV) as a single dose in healthy adult volunteers	Incidence and severity of abnormal physical exam findings, serum chemistries and hematology, vital signs (temperature, blood pressure, heart rate), adverse events (AEs), and incidence of serious adverse events (SAEs)
Secondary	
To characterize the pharmacokinetics (PK) of a single IV infusion of TRL345 overall and by dose group (DG)	$C_{max}$ , $C_{min}$ , CL, $V_{ss}$ , and $t_{1/2}$ , overall and by DG will be calculated by using serum concentrations of TRL345 determined by an enzyme-linked immunosorbent assay (ELISA)
To assess the immunogenicity of TRL345 as measured by anti-drug antibodies (ADAs)	Incidence of baseline and investigational product (IP)-emergent ADA (i.e., anti-TRL345 antibodies) in serum will be determined by an ELISA method.

Objectives	Endpoints
Exploratory	
To explore the pharmacodynamics (PD) of TRL345 in an ex vivo study using serum samples to explore the capacity of various concentrations of TRL345 to neutralize human cytomegalovirus (HCMV) in human serum*	The proportion of samples with TRL345 concentrations within prespecified ranges that are associated with neutralization of HCMV in human serum
To explore if there are any differences in AEs, clinical labs, or PK across DGs to explore if there are any signs of off-target binding of TRL345	Gastrointestinal and central nervous system (CNS) AEs will be compared across DGs for any qualitative or quantitative differences in such events. Lactic acid dehydrogenase (LDH), high-sensitivity C-reactive protein (hsCRP), interleukin (IL)-1alpha, estimated AUC, and estimated t 1/2 will also be compared across DGs.

Note: \* This objective is not covered by this SAP as this analysis will not be performed by Celerion. The results for this objective will not be reported in the Celerion provided CSR.

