Serum samples ADA analysis will be taken on Days 1, 8, 29, 43, and 76 for measurement of anti-TRL345 antibody levels. Samples taken on Days 1, 43, and 76 will be analyzed using an ELISA method. Samples collected on Days 8 and 29 will be held for exploratory analysis, if warranted, based on Day 43 and Day 76 ADA analysis results. The proportion of subjects with detectable anti-TRL345 antibody responses prior to dosing and IP-emergent anti-TRL345 antibodies will be reported.

Serum samples for PD assessment will be collected on Days 1 (pre-infusion and 1 hour after start of infusion), 15, 29, 43, and 76 for ex vivo PD assessments, which will be conducted at [name] lab as defined in a separate protocol, whereby the dosed participants of the study will remain anonymous.

Additional serum samples will also be obtained on Days 1 (pre-infusion), 3, 8, 15, 29, and 43 for possible additional exploratory analyses that may be necessary to further explore any unexpected safety or tolerability observations.

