## **7.2 Immunogenicity Concentrations**

### **Measurements and Collection Schedule**

Blood samples for ADA will be collected and analyzed for all subjects at the following time points:

- Day 1: Baseline
- Days 8 (168 hours post-SOI), 29 (672 hours post-SOI), 43 (1008 hours post-SOI), and 76 (1800 hours post-SOI)

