Treatment P: A single 1-hour intravenous infusion of matching placebo (Dose Groups 1 and 2)

Baseline is the last measurement collected prior to start of dosing.

Overall indicates the number of subjects who had a ADA positive result at one or more time points.

Percentage is relative to the number of subjects (N) dosed.

ADA = Anti-drug antibody; ADA positive = Subject with a confirmed positive ADA result

Program: /CAXXXXX/sas\_prg/stsas/tab\_PROGRAMNAME.sas DDMMYYYY HH:MM

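### The SAP neither derives nor tabulates IP-emergent ADA, half of the secondary immunogenicity endpoint; its only summary across visits is an any-time prevalence that includes baseline positives

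*SAP*

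**What the plan says.** SAP section 2 gives the secondary endpoint as "Incidence of baseline and investigational product (IP)-emergent ADA (i.e., anti-TRL345 antibodies) in serum". Protocol section 2.2.3 has the same two parts. Protocol section 3.1 and SAP section 3 both add that the pre-dose and the IP-emergent proportions will be reported.

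The analysis text is narrower. SAP section 7.3 plans counts and percentages of ADA presence by treatment, at baseline and at each later visit. The in-text shell (Table IIST, SAP 11.1) and the post-text shell (Table ADAD, SAP 11.3) follow that layout and add an Overall category. The IIST footnote defines it: "Overall indicates the number of subjects who had a positive ADA result at one or more time point". ADAD carries the same rule. Both shells state the denominator: "Percentage is relative to the number of subjects (N) dosed". Both are titled for the Immunogenicity Population, which SAP section 4 defines as Safety Population subjects with at least one ADA sample.

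On testing, SAP section 3 says: "Samples collected on Days 8 and 29 will be held for exploratory analysis, if warranted, based on Day 43 and Day 76 ADA analysis results". SAP section 7.2 lists Days 1, 8, 29, 43 and 76 under the statement "Blood samples for ADA will be collected and analyzed for all subjects at the following time points".

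SAP section 9, which records departures from the protocol, does not mention the IP-emergent analysis.

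**The concern.** IP-emergent status is a comparison within a subject: what appeared or rose after dosing, relative to that subject's own baseline. The plan only counts positives visit by visit and then pools them. A team that followed the SAP to the letter would finish with no pre-specified IP-emergent incidence. The Overall row would be the nearest substitute, and it answers a different question.

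With 6 active subjects per dose group, a single pre-dose reactor is enough to make that substitute misleading. If the IP-emergent rule is instead chosen after the listings have been seen, it is no longer pre-specified. Protocol section 8.2 allows ad hoc analyses to support only hypotheses for later trials.

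The denominator adds a second problem. If Day 8 and Day 29 samples stay in the freezer, or only some are assayed, a percentage of subjects dosed does not show how many subjects were tested at those visits.

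**Working it through.** The documents state no ADA rate, so there is no planned figure to reproduce. The check compares the endpoint with the shells and then sizes the difference.

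**Inputs.** SAP section 3: two dose groups, each with 6 active and 2 placebo. That gives 6 per active column, 12 in Active Total, 4 in pooled placebo and 16 in all. Baseline reactivity (q) is not in the documents; 5% is assumed, with a range of 2% to 10%.

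**Step 1: endpoint against shells.** The baseline half has its own row in both tables. The IP-emergent half has none. There is no rule for a negative baseline followed by a post-dose positive, none for a titre rise in a baseline-positive subject, and no requirement for a paired baseline and post-dose result.

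**Step 2: numerator.** Take one subject who is positive at baseline only, with nobody IP-emergent.

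| Column | n | Overall row | IP-emergent |
|---|---|---|---|
| 1 mg/kg or 10 mg/kg | 6 | 1/6 = 17% | 0/6 = 0% |
| Active Total | 12 | 1/12 = 8% | 0/12 = 0% |
| Pooled placebo | 4 | 1/4 = 25% | 0/4 = 0% |

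With one baseline-only positive and one true IP-emergent subject in a group of 6, Overall is 2/6 = 33% and IP-emergent is 1/6 = 17%.

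**Step 3: how likely is such a subject?** The chance of at least one baseline positive among n subjects is 1 − (1 − q)^n.

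| q (assumed) | n = 6 | n = 12 |
|---|---|---|
| 2% | 1 − 0.98^6 = 11% | 1 − 0.98^12 = 22% |
| 5% | 1 − 0.95^6 = 26% | 1 − 0.95^12 = 46% |
| 10% | 1 − 0.90^6 = 47% | 1 − 0.90^12 = 72% |

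The chance and the shift must be paired at the same n. At 5%, a given dose group has a 26% chance of a shift of at least 17 points. Active Total has a 46% chance of a shift of at least 8 points. Strictly, this is the chance of a baseline positive. Such a subject inflates Overall relative to IP-emergent unless he or she also meets a titre-rise rule.

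**Step 4: denominator.** One positive with one of six subjects untested is 1/6 = 17% of those dosed and 1/5 = 20% of those tested. With two untested it is 17% against 1/4 = 25%. If the hold in SAP section 3 applies and nothing is assayed, the Day 8 and Day 29 rows of Table IIST would show 0/6 = 0% with nobody tested. SAP section 8 does call for reduced denominators when data are missing, but that rule sits in the Safety section and the ADA footnotes state a different one.

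**The case against.** Several points on the other side stand.

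- **The Overall row is openly defined.** It is never labelled IP-emergent, and its footnote says what it counts. A reader might infer that the endpoint will be misreported. The documents support only that the IP-emergent half is not derived.
- **A baseline-only positive is not shown as positive after dosing.** That subject appears in the Baseline and Overall rows and in no post-dose visit row.
- **Titres are not hidden.** ADAD tabulates titre categories at each visit, and Appendix 16.2.5.6 lists confirmatory results and titres by subject. It would therefore be wrong to say that a boosted response cannot be told from an unchanged one. That is true of Table IIST alone. For 16 subjects the comparison could be made by hand; what is missing is the rule.
- **Subtraction partly works.** If every baseline is evaluable, Overall minus Baseline gives the number of newly positive subjects. No table says so, it fails when a baseline is missing, and it cannot find a titre rise in a baseline-positive subject.
- **ADAD has an Unevaluable row.** It may separate untested subjects from negatives, so it is not established that ADAD counts untested subjects as negative. But the row is undefined, leaves the denominator unchanged and is absent from IIST.
- **Tested-only percentages are not automatically right.** Suppose Day 29 is assayed in 2 of 6 subjects and both are positive. It is tempting to call 2/6 = 33% wrong and 2/2 = 100% true. Samples are released according to Day 43 and Day 76 results, so the 100% comes from a selected pair, and 33% may be nearer the truth.

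The absence of an IP-emergent rule and row, the contradiction between SAP sections 3 and 7.2, and the silence of SAP section 9 remain unanswered.

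**Conclusion.** The point holds as a gap in the plan that should be fixed. Half of a stated secondary endpoint has no derivation and no table row, and its omission is not declared. The Overall row cannot stand in for it: one baseline-only positive moves it by 17, 8 or 25 points (dose group, Active Total, pooled placebo) with no emergent response at all.

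How often this would happen rests entirely on the assumed baseline reactivity. At 5% (range 2% to 10%) the chance of at least one baseline positive is 26% (11% to 47%) in a group of 6 and 46% (22% to 72%) among the 12 active subjects. With no baseline positives and complete testing, Overall equals the IP-emergent count.

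The denominator problem depends on which testing statement governs. Under SAP section 7.2 it is confined to sporadic missing results. Under the hold in SAP section 3, Table IIST cannot distinguish untested from negative at Days 8 and 29.

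This is a descriptive endpoint in 16 subjects with full listings, so the weight is moderate: a pre-specified comparison is missing, not data.

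**What to change.** 1. Define IP-emergent ADA in SAP section 7.3: a confirmed post-dose positive after a negative baseline or, for a baseline-positive subject, a post-dose titre rise above a stated threshold. The documents give no basis for a particular fold-rise, so set it in advance from the assay's dilution scheme and variability.
2. Add an IP-emergent row to Tables IIST and ADAD. Relabel Overall as any-time prevalence including baseline, or restrict it to post-baseline visits.
3. Use subjects with an evaluable result at the visit as denominator. For IP-emergent ADA, require an evaluable baseline and at least one evaluable post-dose result. Define unevaluable, and keep it separate from not tested.
4. Reconcile SAP section 3 with section 7.2. If Day 8 and Day 29 samples are tested selectively, print only the numbers tested and positive, with no percentage.
5. Separately, settle the ADA assay. Protocol section 3.1 says "Samples taken on Days 1, 43, and 76 will be analyzed using an electrochemiluminescence assay", while Protocol section 2.2.3 says "Incidence of baseline and IP-emergent ADA (i.e., anti-TRL345 antibodies) in serum will be determined by ELISA". The SAP uses ELISA throughout. This does not affect the derivation, but the documents should agree.

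The cost is SAP wording, two table shells and a short protocol clarification of the assay. Items 1 to 3 need no new sample or procedure. Item 4 adds laboratory work only if the sponsor decides to assay every Day 8 and Day 29 sample. The changes should be in place before the SAP is finalised and the database locked.
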